4.10 Rationale for Study Design

Retrospective-observational studies are required to describe population treated in the daily practice, the use of the drug and its effect and safety in real life conditions.

4.11 Rationale for centralized MRI measurements

It is customary for any multi-center clinical trial to collect MRI scans from various scanner manufacturers (General Electric, Siemens and Philips mainly), as is also the rule in the clinical practice. Although there are subtle technical differences in the implementation of each MRI pulse sequence, the outcome (e.g. the MR images) is extremely similar from a visual standpoint whatever the origin. This would therefore not introduce a bias in the analysis for qualitative assessments (bone disease scoring). For quantitative assessments (organ volumes), specific efforts are made when setting up the MRI protocol at each site in order to minimize the variability across sites, and allow accurate measurements.

When it comes to assessing longitudinal changes (either qualitatively or quantitatively), it is highly preferable to impose that the exact same scanner and scanning parameters be used from one visit to the other at a given site. Such requirement is reminded to the MRI facilities within the study imaging guidelines, and verified upon image QC at BioClinica.

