4 STUDY PLAN

4.1 Data collection and transmission

All data entered will be used for analysis purposes and results will be submitted to inform regulatory agencies. Patient care and management is freely determined by the participating physician, in the framework of an observational study reflecting the daily medical practice. The clinical data, the results of routine clinical and laboratory testing that are part of standard medical care for patients with Gaucher disease will be collected from the medical record of the patient :

- Socio-demographic characteristics
- History of the disease and context of diagnosis
- Medical background
- MRI: abdominal and bone, as defined below
- Clinical data available in the range from 3 months before or after each MRI
- Biological data available in the range from 3 months before or after each MRI
- Treatment with VPRIV® (velaglucerase alfa), including the doses and regimens

4.2 The MRI images collected during the study:

The MRIs performed in the patient's usual medical follow-up for its Gaucher disease (abdominal MRI (liver and spleen) and bone MRI (back injury pelvis, lower limbs) and / or whole-body MRI) will be collected. Among the MRIs available in the patient's medical records, MRIs will be collected the following:

- Reference MRI: MRI closest to the date of initiation of VPRIV® in the five years preceding the start of treatment or within three months after initiation of VPRIV®.
- MRIs of the retrospective phase of the study: All MRIs available between the reference MRI and the inclusion date of the patient.
- MRIs of the prospective phase of the study: all the MRIs that will be realized during the prospective phase of the study, that is to say, during the year following the date patient inclusion in the study.

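### Section 4.11 rules out scanner bias in bone scoring without support and relies on a same-scanner requirement that cannot reach the archived scans in the before/after comparison

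*Protocol*

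**What the plan says.** Section 4.11 of the Protocol makes three statements about scanners.

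- On mixing manufacturers, it concedes small differences in pulse sequences but holds that the images look nearly alike, and concludes: "This would therefore not introduce a bias in the analysis for qualitative assessments (bone disease scoring".
- On organ volumes, it says that "specific efforts are made when setting up the MRI protocol at each site in order to minimize the variability across sites".
- On change over time, whether qualitative or quantitative, it says that "it is highly preferable to impose that the exact same scanner and scanning parameters be used from one visit to the other". It continues: "Such requirement is reminded to the MRI facilities within the study imaging guidelines, and verified upon image QC at BioClinica".

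The primary endpoint (section 3.1) is the change in BMB score from the baseline MRI to follow-up MRIs.

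Section 4.2 describes the images as "The MRIs performed in the patient's usual medical follow-up for its Gaucher disease". The reference scan is the "MRI closest to the date of initiation of VPRIV® in the five years preceding the start of treatment or within three months after initiation of" the study drug. The retrospective scans are "All MRIs available between the reference MRI and the inclusion date of the patient". Section 4.12 runs the retrospective period from the baseline MRI to inclusion, gives one MRI every 2 years as current practice, and lets the final MRI fall in the year before or the year after inclusion. Section 4.1 leaves patient management to the physician.

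Section 8.5 compares pre- and post-treatment BMB by the Wilcoxon signed-rank test, on all assessable MRIs and again on those of optimal quality. Section 8.6 repeats this split for the MRI parameters.

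**The concern.** The two paragraphs of section 4.11 pull against each other on the comparison that matters most. The first dismisses scanner bias in bone scoring. The second says the same scanner matters for longitudinal change, qualitative scoring included, and the primary endpoint is a longitudinal change in a qualitative score.

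The control described also belongs to a prospective imaging trial. Study guidelines can influence scans still to be taken, not scans already in the archive. The reference scan is always earlier than the follow-up scans and may date from up to five years before VPRIV was started. A scanner or sequence replaced in the meantime would therefore separate before from after. The BMB items are graded from T1 and T2 signal intensity (sections 6.6 and 6.7), so a change in acquisition could plausibly move a grade by one step.

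The study has no untreated comparison group, and section 1.3 expects the data to help assess the impact of treatment. A systematic acquisition effect would be read as change under VPRIV.

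**Working it through.** The protocol states no figure on this point, so there is none to reproduce. The check sets the sections side by side and then illustrates the stakes under stated assumptions.

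**Which scans can the guidelines reach?**

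| Scan | Timing | Within reach of study guidelines? |
|---|---|---|
| Reference | up to 5 years before, or 3 months after, VPRIV start; opens the retrospective period | No |
| Retrospective follow-up | between reference and inclusion | No |
| Final | year before or year after inclusion | Only if after inclusion |
| Prospective | year after inclusion | Yes, as far as routine care allows |

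At one MRI every 2 years, a one-year prospective phase yields about 1/2 = 0.5 scan per patient, against at least one archived scan each. Every before/after pair has at least its first scan outside the guidelines. Where the final MRI precedes inclusion, both scans are outside.

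**What happens when QC finds a difference?** Section 4.11 says QC verifies the requirement but states no consequence. The read-out fields in sections 6.6 and 6.7 include a technical adequacy grade and reasons for each region, but no scanner or sequence item. The optimal grade is given scan by scan, on coverage, artifacts and compliance with the imaging protocol. It does not name the same scanner across visits.

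**How much could it matter?** From the protocol: n = 40 to 50 (section 8.2). Assumed: two-sided 5% level, no true treatment effect, and the size of the shift.

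(a) Let d be the systematic before/after shift divided by the SD of change. The false-positive probability of a paired test is approximately 1 − Φ(1.96 − d√n) + Φ(−1.96 − d√n). For d = 0.2 and n = 40, d√n = 0.2 × 6.325 = 1.265, which gives 0.244.

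| d | n = 40 | n = 50 |
|---|---|---|
| 0 | 5.0% | 5.0% |
| 0.1 | 9.7% | 10.9% |
| 0.2 | 24.4% | 29.3% |
| 0.3 | 47.5% | 56.4% |
| 0.5 | 88.5% | 94.2% |

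(b) Simulated signed-rank test (4,000 runs per setting) on changes rounded to whole points, where a share of patients carries a 1-point scanner shift in the same direction:

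| SD of change | Share shifted | n = 40 | n = 50 |
|---|---|---|---|
| 1 | 25% | 26% | 33% |
| 1 | 50% | 76% | 85% |
| 2 | 25% | 10% | 12% |
| 2 | 50% | 31% | 38% |

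When the 1-point shift is random in sign, the rejection rate stays at 4 to 6% in every setting. That is added noise, not bias.

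(c) On the scale of the mean: if half the pairs change scanner and each shifts by 0.2 to 0.5 points, the bias is 0.5 × 0.2 = 0.10 to 0.5 × 0.5 = 0.25 points. With n = 45 and SD 1, the 95% interval has half-width 1.96/√45 = 0.29. All inputs here except n are assumed; 45 is the midpoint of the expected range.

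**The case against.** Several points on the other side stand.

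- A reader might infer that the protocol claims to have imposed one scanner throughout. It does not: the wording is a strong preference, then a requirement that is reminded and verified. Verification is possible on archived images, and the guidelines can reach prospective scans.
- A reader might infer that scanner change does coincide with before/after. The documents give no data on scanner changes. The time order makes confounding possible, not certain, and bias also needs a common direction across patients from different centres.
- The no-bias sentence closes a paragraph about mixing manufacturers across centres; longitudinal change is taken up separately. This supports limiting the sentence to cross-sectional scoring. It does not support leaving it unqualified when the endpoint is a change score.
- The optimal-quality analysis is a partial safeguard. Optimal requires compliance with the imaging protocol, so a changed scanner or sequence might already downgrade a scan. The imaging guidelines are not shown, so this is unsettled; as defined, two optimal scans from different scanners would both qualify.
- BMB items are relative grades by their wording, which may limit sensitivity to the scanner. The documents do not show how far.
- A reader might infer that volumes and BMB share the same images. Section 4.2 separates abdominal from bone MRI, with whole-body MRI as an alternative or addition.
- A sensitivity analysis is ordinary SAP content, and section 8.1 defers the detailed plan. Its absence here is not the defect. The defects are what section 4.11 asserts and the lack of a stated scanner or sequence record for each scan.

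**Conclusion.** The point holds in limited form. Section 4.11 excludes a bias that the protocol neither measures nor, for archived scans, can prevent, and its own next paragraph says the same scanner matters for the kind of change that forms the primary endpoint. Scanner or sequence change may be confounded with before versus after, and the optimal-quality analysis covers this only in part.

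The size is unknown. The figures above rest on assumed shifts and SDs and on a shift in one direction; they show that a modest systematic shift would matter at n = 40 to 50, not that one exists. The documents do not support the conclusion that the results will be biased. The point calls for a correction of wording and a small addition to data capture and analysis; it does not invalidate the design.

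**What to change.** 1. In section 4.11, delete the no-bias sentence or limit it to cross-sectional scoring.
2. State that the same-scanner requirement can apply only to prospective scans, as far as routine care allows, and that for archived scans QC can only detect a difference.
3. Have the existing QC check record scanner and T1/T2 sequence for every scan, so that each before/after pair can be classed as same or different.
4. Add a sensitivity analysis of BMB change and of organ volumes restricted to same-scanner, same-sequence pairs, each classed on its own images.
5. Report the change in differing pairs descriptively only. With an assumed 22 and 23 pairs and SD 1, the difference between the two groups has SE √(1/22 + 1/23) = 0.30 and a 95% half-width of 1.96 × 0.298 = 0.58, wider than the assumed 0.2 to 0.5 point shift. A test would have power of about 10% at 0.2 and 39% at 0.5, so a null result would not be reassuring.

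The cost is a few recorded fields, on items that section 4.11 says QC already verifies, and one extra analysis. The restricted subset will be smaller and its intervals wider, so it belongs beside the main analysis and not in its place.

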4.12 Study Duration

The study is developed in conjunction with the French Referral Centers of Lysosomal Diseases, and the French Gaucher Treatment and Evaluation Committee (CETG: Comité d'Evaluation du Traitement de la maladie de Gaucher). It is a retro prospective observational study of the French cohort of patients with type 1 Gaucher disease treated with VPRIV® in everyday clinical practice.

It consists of two phases: a retrospective and a prospective phase with a 1 year inclusion period.

Phase I: retrospective phase

The retrospective period includes the period between the date of the baseline MRI to the patient's date of inclusion in the study. The reference MRI is defined as the closest MRI to the initiation of VPRIV®, within the past five years, or within three months after initiation of VPRIV®.

Phase II: prospective phase

Prospective period will be one year from the date of patient inclusion in the study.

The final MRI

MRI being performed in current practice every 2 years, the final MRI follow-up performed corresponds to those in the previous year or in the year following the patient's inclusion.

The duration of the study will be 2 years: a 1-year inclusion period to be sure to include all patients treated with VPRIV® (reviewed annually in consultation each year) and a prospective follow-up period of 1 year. Provisional timetable for the study:

CCTIRS / CNIL authorization	October 23, 2015
Inclusion of the first patient in the study	September 30, 2016
Inclusion of the last patient in the study	September 30, 2017
Last visit of the last patient	September 30, 2018
Study clinical report	January 31, 2019

5 STUDY POPULATION

To reflect the daily practices, this study includes all patients with a confirmed diagnosis of Type 1 Gaucher disease treated with VPRIV® at the date of beginning of the study and who meet the selection criteria of the study.

5.1 Inclusion Criteria

1. Patients of any age or gender with confirmed diagnosis of type 1 Gaucher disease,
2. Patients treated with VPRIV® at the beginning of the study. Prior starting VPRIV® patients could be either treatment naïve or previously treated with any other Gaucher treatment than VPRIV®.
3. Patients should have one MRI data in the 5 previous years before starting VPRIV® treatment
4. Informed written consent obtained from the patient, and/or patient's parent(s), and/or legal representative. Assent, if old enough to grant, will be obtained from all patients under the age of 18 years.

5.2 Exclusion Criteria

1. Patients for whom MRI is contra-indicated
2. Patients who did not have an MRI during the five years prior to the initiation of treatment with VPRIV® or within three months after initiation of VPRIV®
3. Patients included in an ongoing clinical trial where the product is blinded

5.3 Withdrawal of Patients from the Study

Patients are free to withdraw from the study at any time without having to justify their decision and without any consequences for their quality of care and the quality of their relation with their treating physician. However, if possible the reason of the withdrawal will be asked and recorded.

6 STUDY PROCEDURES

6.1 Informed Consent

It is the responsibility of the Investigator to obtain written Informed Consent and assent, where applicable from study patients. All consent and assent documentation must be in accordance with applicable regulations and GCP. Each patient or the patient's legally authorised representative as applicable is requested to sign the Patient Informed Consent

Form or a certified translation, if applicable after the patient has received and read (or been read) the written patient information and received an explanation of what the study involves, including but not limited to: the objectives, potential benefits and risk, inconveniences and the patient's rights and responsibilities. A copy of the informed consent and assent documentation (i.e., a complete set of patient information sheets and fully executed signature pages) must be given to the patient or the patient's legally authorised representative. If applicable, it is provided in a certified translation of the local language. Signed consent forms must remain in each patient's study file and must be available for verification at any time.

The Principal Investigator provides the Sponsor with a copy of the consent form (and assent form where applicable) which was reviewed by the IRB/IEC and which received their favourable opinion/approval. A copy of the IRB/IEC's written favourable opinion/approval of these documents must be provided to the Sponsor, prior to the start of the study unless it is agreed to and documented (abiding by regulatory guidelines and national provisions) prior to study start that another party (i.e., sponsor or Coordinating Principal Investigator) is responsible for this action. Additionally, if the IRB/IEC requires modification of the sample, Patient Information and Consent document provided by the Sponsor, the documentation supporting this requirement must be provided to the Sponsor.

6.2 Institutional Review Board or Independent Ethics Committee

For investigator sites outside the EU, it is the responsibility of the Investigator to submit this protocol, the informed consent document (approved by the Sponsor or their designee), relevant supporting information and all types of patient recruitment information to the IRB/IEC for review, and all must be approved prior to site initiation.

For investigator sites within the EU and if applicable within a given region the applicant for an IEC opinion can be the Sponsor, the Investigator, or for multicentre studies the Coordinating Principal Investigator or Sponsor, according to national provisions.

Responsibility for coordinating with IRBs/IECs is defined in the Investigator/Sponsor (CRO) Contract.

Prior to implementing changes in the study, the Sponsor and the IRB/IEC must approve any revisions of any revised informed consent documents and amendments to the protocol unless there is a patient safety issue.

For investigator sites outside the EU, the Investigator is responsible for keeping the IRB/IEC apprised of the progress of the study and of any changes made to the protocol, but in any case at least once a year. For investigator sites within the EU and if applicable within a given region, this can be done by the Sponsor, the Investigator or for multicentre studies the Coordinating Principal Investigator, according to national provisions. The Investigator must also keep the local IRB/IEC informed of any serious and significant AEs.

6.3 Study Entrance Criteria

At screening, each patient will be reviewed for eligibility against the study entrance criteria. Patients who do not meet the study entrance criteria will not be allowed to participate in the study. The reason(s) for the patient's ineligibility for the study will be reviewed during remote and/or on-site monitoring visits (investigating the number of patients expected at the site vs. the number observed in the database).

6.4 Confirmation of Study Eligibility

Patient eligibility according to the study inclusion and exclusion criteria will be confirmed at Baseline on the basis of review of the study entrance criteria.

6.5 Demographics

Patient demographic information including gender, age, and professional status will be collected as soon as the patient is included in the observational study. The age that will be collected is the age of patient at VPRIV® treatment initiation.

6.6 Medical History

For the retrospective part of the study, medical past history are collected by the physician from the medical record of the patient. On the CRF are reported:

- Socio-demographic and clinical characteristics of patients with Gaucher's disease
- All medical past history of the patient: nature, beginning date, end date or ongoing and relationship to Gaucher disease
- Family past history : nature and family link
- The description of the history of the disease : year of first symptoms, nature of the first symptoms, diagnostic year, nature of the laboratory examination which has confirmed the diagnosis (enzyme assay, molecular biology (genotyping), bone marrow, bone marrow biopsy, liver biopsy, histology of the spleen, other), value of the enzyme assay, phenotype and genotype
- The clinical and biological status within the 6 months period : 3 months before the MRI - 3 months after the selected MRI which is the closest available one to the VPRIV® initiation
- The clinical and biological status of the patients when the VPRIV® treatment was initiated
- The standardized measures issued from the standardized review of the MRI by Bioclinica centralized laboratory. The review is conducted on the MRI that the treating physician addresses via the CETG to a central review radiological center after anonymisation of the documents

The quality of the MRI is evaluated and classified in three categories: Optimal, sub optimal and not assessable according the following definition:

- Optimal: Sufficient anatomical coverage, good image quality with no to minimal image artifacts and compliance with the imaging protocol
- Suboptimal: Sufficient anatomical coverage, presence of moderate image artifacts and/or minor deviations to the imaging protocol, with minimal impact on the analysis

***Retrospective and prospective observational study of MRI changes in bone and visceral lesions of patients with type 1
Gaucher disease treated with VPRI[®] (velaglucerase alfa)***

- Not assessable: Insufficient anatomical coverage and/or presence of strong image artifacts and/or severe deviations to the imaging protocol, which would lead to an unreliable analysis.

Spleen/Liver:

TEST	DESCRIPTION	FORMAT/VALUES
ABDO_TECH_AD	Technical Adequacy for Abdominal MR data	0 = Optimal 1 = sub optimal 2 = Not assessable
ABDO_TECH_REASON	Reasons for Abdominal MR images not being optimal	List of reasons separated by a
SPLEEN_VOL	Spleen Volume (mm ³)	FLOAT
LIVER_VOL	Liver Volume (mm ³)	FLOAT
SPLEEN_COV	Full Spleen Coverage achieved	Y/N
LIVER_COV	Full Liver Coverage achieved	Y/N
SPLEEN_INF	Presence of Infarcts	Y/N
SPLEEN_FD	Presence of Filling Defects	Y/N
LIVER_INF	Presence of Infarcts	Y/N
LIVER_FD	Presence of Filling Defects	Y/N

Spine/Femur:

TEST	DESCRIPTION	FORMAT/VALUES
SPINE_TECH_AD	Technical Adequacy for Spine MR data	0 = Optimal 1 = sub optimal 2 = Not assessable
SPINE_TECH_REASON	Reasons for Spine MR images not being optimal	List of reasons separated by a
SPINE_BMB_T1	Spine BMB score of T1-weighted	0 = Slightly hyper intense 1 = Isointense 2 = Slightly hypo intense 3 = Hypo intense 4 = N/A
SPINE_BMB_T2	Spine BMB score of T2-weighted	0 = Iso intense 1 = Slightly hypo intense 2 = Slightly hyper intense 3 = Hypo intense 4 = Hyper intense 5 = N/A

***Retrospective and prospective observational study of MRI changes in bone and visceral lesions of patients with type 1
Gaucher disease treated with VPRIV® (velaglucerase alfa)***

SPINE_BMB_INFILTR	Spine BMB score for Infiltration Pattern	0 = None 1 = Patchy 2 = Diffuse 5 = N/A
SPINE_BMB_FAT	Assessment of Spinal Fat in Basivertebral Region	3 = Preservation of fat 4 = Absence of fat 5 = N/A
SPINE_COMMENTS	Free Comments on Spine Scoring	
FEMUR_TECH_AD	Technical Adequacy For Femur MR Data	0 = Optimal 1 = Readable, but not optimal 2 = Not readable
FEMUR_TECH_REASON	Reasons for Femur MR images not being Optimal	List of reasons separated by a
FEMUR_BMB_T1	Femur BMB Score of T1-weighted	0 = Slightly hyper intense or isointense 1 = Slightly hypo intense 2 = Hypo intense 3 = N/A
FEMUR_BMB_T2	Femur BMB Score of T2-weighted	0 = Isointense 1 = Slightly hypo intense 2 = Slightly hyper intense 3 = Hypo intense 4 = Hyper intense 5 = Mixed type 6 = N/A
FEMUR_BMB_SITE	Femur BMB Score for sites of involvement	0 = No site of involvement 1 = Diaphysis 2 = Proximal epiphysis / apophysis 3 = Distal epiphysis 4 = N/A
FEMUR_COMMENTS	Free comments on Femur scoring	

Posology at initiation: UI/kg/2 weeks, UI/kg/3 weeks, UI/kg/1month

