3 STUDY ENDPOINT

3.1 Primary Endpoint(s)

The primary endpoint is the change over time between the baseline MRI and the follow-up MRIs, of the BMB score (11) weighted at T1 and T2 and measured at the femur and lumbar spine .

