8.5 Primary Endpoint(s) or Assessments

The changes pre and post treatment with velaglucerase alfa of the spine and femur BMB score will be described and compared using Wilcoxon signed-rank test. The analysis will be conducted successively on all MRI assessable and on optimal quality MRI only.

Primary Safety Endpoint(s)

Adverse events will be coded using MedDRA and described as recommended in ECH procedures as far as possible due in particular to retrospective conditions..

Primary Efficacy/Effectiveness Endpoint(s)

The values observed at the different follow up times and the variations between the reference MRI and the follow-up MRI, of the BMB weighted score at T1 and T2 measured at the femur and lumbar spine, are described by mean and standard deviation and the 95% confidence interval will be calculated. These values will be compared at the different follow up times with test on repeated data: ANOVA on repeated series or Wilcoxon rank test, depending on the nature and distributions of the studied variables.

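### The primary analysis takes means and tests of T2 BMB fields whose category codes are not an ordered severity scale, and no conversion to points is stated

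*Protocol*

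**What the plan says.** Protocol section 3.1 defines the primary endpoint as the change from the baseline MRI to the follow-up MRIs in the "BMB score (11) weighted at T1 and T2", taken at the femur and lumbar spine. The number 11 is a literature reference. Section 8.5 then says that the values and changes "of the BMB weighted score at T1 and T2 measured at the femur and lumbar spine, are described by mean and standard deviation", with a 95% confidence interval, and that they are compared over time by repeated-measures ANOVA or a Wilcoxon test. The opening sentence of 8.5 says that the "spine and femur BMB score will be described and compared using Wilcoxon signed-rank test".

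The fields are tabulated in 6.6, and the table is repeated in 6.7:

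- Spine T1: slightly hyperintense 0, isointense 1, slightly hypointense 2, hypointense 3, N/A 4.
- Femur T1: slightly hyperintense or isointense 0, slightly hypointense 1, hypointense 2, N/A 3.
- Spine T2: isointense 0, slightly hypointense 1, then "2 = Slightly hyper intense 3 = Hypo intense 4 = Hyper intense 5 = N/A".
- Femur T2: the same codes 0 to 4, then mixed type 5 and N/A 6.
- Spinal fat: "3 = Preservation of fat 4 = Absence of fat 5 = N/A".
- Femur site: "0 = No site of involvement 1 = Diaphysis 2 = Proximal epiphysis / apophysis 3 = Distal epiphysis 4 = N/A".

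The protocol states no conversion of these codes to points and no region score or total. Section 4.3 lists the BMB score among the quantitative data from the central reading, while 4.11 treats bone disease scoring as a qualitative assessment.

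**The concern.** A mean needs codes whose steps mean something, and a signed-rank test needs at least codes whose direction means something. The two T2 fields, which are half of the four T1/T2 fields in the primary endpoint, have neither property as printed. Going up the T2 code list, signal moves below isointense, above it, below it and above it again, and femur T2 ends in a mixed category. If the numbers are analysed as they stand, the T2 part of the primary result depends on the order in which the categories were listed.

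There is a second, smaller gap. N/A carries the highest number in every BMB field, and it is recorded per field, whereas technical adequacy is graded per body region. A spine examination graded assessable but lacking a T2 sequence would carry spine T2 = 5, and no sentence makes that value missing.

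Section 4.1 says that the results will be submitted to inform regulatory agencies.

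**Working it through.** The protocol gives no calculated figure to reproduce. Section 8.2 expects 40 to 50 patients without a formal calculation. The check is therefore whether the printed T2 codes behave as a scale under any plausible reading of severity. The protocol does not define severity for T2 signal, so each reading below is an assumption.

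**All moves between spine T2 categories.** Five categories without N/A give 5 × 4 = 20 ordered moves. For each, the change in code is compared with the change in severity.

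| Assumed severity | Wrong sign | Code change with no severity change | Right sign, wrong size | Correct |
|---|---|---|---|---|
| Distance from isointense (0, 1, 1, 2, 2) | 0 | 4 | 12 | 4 |
| Higher signal is worse | 8 | 0 | 10 | 2 |
| Lower signal is worse | 12 | 0 | 6 | 2 |

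The last column is 20 minus the other three. None of the three readings makes the codes usable as numbers. Under the distance reading the four false changes are 1 to 2, 2 to 1, 3 to 4 and 4 to 3.

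**What this can do to the primary result (distance reading).** Take 45 patients, the middle of 40 to 50. Let 6 move from slightly hypointense (1) to slightly hyperintense (2) and the rest stay where they are. Severity is unchanged in everyone.

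- Mean change in code = 6/45 = +0.13 (6/50 = +0.12 to 6/40 = +0.15 over the expected range).
- SD of change = √(6/45 × 39/45 × 45/44) = 0.34. The normal-approximation 95% CI is 0.133 ± 1.96 × 0.344/√45 = 0.133 ± 0.100, that is 0.03 to 0.23, which excludes zero.
- Signed-rank test: zero changes drop out and all six remaining differences are positive, so the exact two-sided p = 2 × 0.5⁶ = 0.031, whatever the number of unchanged patients. With five such patients it is 2 × 0.5⁵ = 0.0625.

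The count of six is an illustration. The protocol gives no figure for how often such moves occur.

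**After recoding.** With T2 scored 0, 1, 1, 2, 2, the four false changes become zero. This scoring is used only for the check; it is not taken from the protocol or from reference 11.

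**T1 fields.** Spine T1 (0 to 3) and femur T1 (0 to 2) each run in one direction of signal. A Wilcoxon test on them is interpretable once N/A is removed.

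**N/A codes.** They are 4 (spine T1), 5 (spine T2, infiltration, fat), 3 (femur T1), 6 (femur T2) and 4 (femur site), the largest number in each list. No size is given for this gap, because the protocol gives no N/A rates and does not say that N/A is counted.

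**The case against.** The strongest reply is that the codes are database labels. The tables have a data-export layout. Fat is numbered 3 and 4 beside infiltration at 0, 1 and 2, and both use 5 for N/A, which looks like labels drawn from one list. Section 3.1 ties the score to a cited publication, and 8.1 announces a detailed analysis plan that could hold the conversion. This stands as far as it goes: it makes the problem a risk in following the text as printed, not proof of what will be done. It does not remove the mismatch. The protocol itself gives T1 and T2 fields the name BMB score and fixes mean, SD and CI for the score of that name. For secondary variables, 8.6 uses frequency and percentage for categorical and ordinal data. The choice between ANOVA and Wilcoxon does not help, since ranks also need ordered codes.

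Several stronger readings are not supported:

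- A reader might infer that the whole primary endpoint is uninterpretable. Both T1 fields are ordered apart from N/A.
- A reader might infer that an unread sequence counts as the worst disease. Nothing says so, and 8.5 limits the analysis to assessable MRI.
- A reader might infer that the sign of the T2 change is always arbitrary. Under distance from isointense no move is reversed; the codes split ties and distort step size. Wrong signs arise only under the directional readings.
- A reader might infer that infiltration, fat and site are excluded from the primary variable. The opening of 8.5 speaks of the spine and femur BMB score without that limit.
- A reader might infer that femur site can hold only one location. The table prints one list of codes, but its description speaks of sites in the plural.

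The primary objective in 2.1 is descriptive. That lowers the weight of any p-value, but a descriptive mean of unordered codes is no easier to interpret.

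**Conclusion.** Wrong as written, for the two T2 fields. The stated codes and the stated summary statistics do not fit together, and the protocol prints no rule to bridge them. Taken from the printed codes, T2 change has the wrong size in 12 of 20 spine moves and is false in 4 of 20 if severity means distance from isointense; it has the wrong sign in 8 or 12 of 20 if severity follows signal in one direction or the other. In the illustration, six of 45 patients produce a mean change of +0.13 with p = 0.03 and no true change. These figures rest on assumed readings of severity and, for the last, on an assumed number of patients. The T1 fields are not affected beyond N/A. The N/A gap is an omission to close, with no bias established.

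**What to change.** Amend 3.1, 6.6, 6.7 and 8.5 together:

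1. State that the numbers in the spine and femur tables are category labels only.
2. Convert each category, including mixed type, to BMB points by the definition in reference 11, and print that conversion in the protocol.
3. Set N/A to missing in every field.
4. State that femur site can record more than one location, with one yes/no item per site.
5. Name the resulting spine score and femur score, and a total if reference 11 defines one, as the primary variable, and say which fields enter each.

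The cost is wording and a recode of fields that the central reading already collects. The one change to data capture is femur site, if it is currently a single choice. The sample size is unaffected.
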